In order to address this important research gap, we propose a randomized controlled trial among pregnant women in Tanzania. Iron deficiency and malaria are major public health problems in Tanzania. More than 90% of the population resides in malaria-endemic regions, and an estimated 1.7 million women are affected by malaria during pregnancy each year [13]. Together, iron deficiency anemia and malaria represent the leading cause of maternal mortality, accounting for over a quarter of all maternal deaths [14]. We propose to enroll women who not anemic and not iron deficient in a placebo-controlled trial to examine the safety and efficacy of 60 mg daily iron prenatal supplement. In light of documented benefits of iron supplementation among anemic women, those who are severely anemic (defined in Tanzania as Hb < 8.5 g/dL) or iron deficient (serum ferritin $< 12 \,\mu$ g/L) will receive iron, as per standard of care, and will not be enrolled in the trial. We will use the cutoff level of < 8.5 g/dL as the threshold for providing iron supplementation to study participants, in accordance with Tanzanian national guidelines. In our study population, the causes of anemia are multifactorial and may include folate deficiency, vitamin B12 deficiency, zinc deficiency, parasitic infections, other chronic infections and inflammations, and hemoglobinopathies such as thalassemia and sickle cell disease [15]. Because we will also be excluding women who are iron deficient at baseline, it is likely that anemia between 8.5 and 11.0g/dL will be largely attributable to these other underlying factors rather than iron deficiency and these participants are unlikely to respond to iron supplementation.

Specific Aims

Primary Aims

- 1. To determine the **safety** of iron supplementation among pregnant Tanzanian women, as measured by (a) **the incidence of placental malaria**, and (b) **placental malaria parasite density**, compared to placebo.
- 2. To determine the **efficacy** of iron supplementation among pregnant Tanzanian women, as measured by **maternal hemoglobin** concentrations, compared to placebo.
- 3. To determine the **efficacy** of iron supplementation among pregnant Tanzanian women, as measured by infant **birth weight**, compared to placebo.

Secondary Aims

1. To determine the **efficacy** of iron supplementation among pregnant Tanzanian women, on the **incidence of maternal anemia**, compared to placebo.

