An internal medical monitor will be hired in Dar es Salaam to ensure that the study design is implemented according to protocol. S/he will be a physician with research training and will undertake regular meetings with the site coordinator and with members of the study staff; review of data collection forms and related records to assess their completeness; observation of the study personnel carrying out specific procedures; review of other documents and files at the site to assess whether they are up-to-date; physical or verbal walk-through of certain procedures; conversations with key support personnel to assess their practices with regard to data collection; and inspection of storage facilities (laboratory and data).

Definition of Main Endpoints

Primary endpoints: These will be the incidence and parasite density of placental malaria. Placental infection status will be categorized as infected if there are asexual parasites in the placenta blood; not infected if the placental blood smear is negative; or status unknown if no placental smear is available. Placental malaria parasite density will be defined as number of parasites per μ L of blood or 200 white blood cells; the latter will be converted to a count per μ L of blood assuming a count of 8000 WBC/µL [155]. The continuous measurements of maternal hemoglobin and birth weight will be two other primary endpoints.

Secondary endpoints: Low birth weight will be defined as birth weight less than 2500 grams. Maternal malaria will be defined in 2 ways: fever within the last 72 hours with any parasitemia on a peripheral blood smear. High density malaria will be defined as fever with parasitemia >5000. Anemia will be defined as hemoglobin less than 11 g/dl. Severe anemia is less than 8.5 g/dl.

Data Analysis

Analysis of primary endpoints: Intent-to-treat analysis of treatment effects will be used as the primary analysis strategy for all endpoints.

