Modification of any treatment effects observed by a third variable, such as gravidity or maternal mid-upper arm circumference, will be explored by stratification and testing for significance of the difference between the treatment effects observed in two strata. For effect modifiers which are continuous or have more than two levels, the logistic regression model will be used to quantify effect modification and test for statistical significance, through the creation of model interaction terms and use of the likelihood ratio test to assess significance. Since there are no *a priori* effect modifiers hypothesized, our study is not designed to detect any which may occur, and we acknowledge that unless there is strong modification of an observed treatment effect, the power of our study to detect these will be quite low.

Placental malaria, defined as a continuous variable of parasite density will be compared between the two treatment arms. The difference in these measurements for the two treatment groups, and the statistical significance of any difference observed will be assessed by a two-sample t-test and non-parametrically by the Wilcoxon rank-sum test. Linear regression models will be used to evaluate effect modification, such as by baseline iron status, or dietary intake by creating appropriate cross-product terms and evaluating their significance by F-tests. To evaluate treatment-related differences in change after adjusting for risk factors which remained imbalanced after randomization, linear regression models of the change variables on treatment status and other risk factors will be used.

Hemoglobin: This parameter will be assessed three times (at baseline, 30 weeks of pregnancy and at delivery). In the primary analyses we will compare the mean change between baseline and delivery. This change will be calculated as the average within-women difference in these measurements for the two treatment groups, and the statistical significance of any difference observed will be assessed by a two-sample t-test and non-parametrically by the Wilcoxon rank-sum test. Linear regression models will be used to evaluate hemoglobin levels between the treatment arms, adjusting for factors that were imbalanced after randomization, and effect modification.

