Power for the primary aims, placental malaria infection and density, maternal hemoglobin levels, and birth weight, have been calculated based on a nominal Type I error rate (alpha) of 0.05, and a 10% sample size adjustment for loss-to-follow-up and fetal loss. Power is based on a 2-sided test of proportions, based on a Z-statistic using the asymptotic variances of the observed proportions. The table below displays the power of the study to detect treatment effects on placental malaria infection. The assumed placebo arm rate of 20-30% is supported by studies reviewed above [37, 39]. Displayed is the power (for treatment effects expressed as % reductions) based on a 2-sided test for comparison of proportions, total enrolled n=1500, with a 10% sample size adjustment to account for loss to follow-up and fetal loss.

Statistical Power for Incidence of Placental Malaria							
Incidence in Placebo Arm	Effect of Intervention on the Incidence						
	HR=0.75	HR=0.70	HR=0.65	HR=0.60			
20%	48%	65%	80%	90%			
25%	57%	74%	87%	95%			
30%	64%	80%	92%	98%			

The study will have good power to detect a 35% effect size, for placental malaria rates as low as 20% in the placebo arm. If the placental malaria rates are larger (25% or 30%), the study will have good power to detect a 30% effect size and excellent power to detect a 40% effect size.

Continuous Variables: The table below displays the power of the study to detect treatment effects on continuous variables, including placental malaria density, maternal hemoglobin concentration, and birth weight. Displayed is the power (for treatment effects expressed as percent changes in effect size) based on a 2-sided test for comparison of proportions, total enrolled n=1500, with a 10% sample size adjustment to account for loss to follow-up.

Placental malaria density: The table below displays the power of the study to detect treatment effects on placental malaria density. The assumed mean placental malaria density in the placebo arm of 9,000 parasites/ μ L is supported by studies reviewed above [156]. The study will have good power to detect an effect size of 8.5%, and excellent power to detect a 10-20% change, based on a 2-sided test for comparison of proportions, total enrolled n=1500, with a 10% sample size adjustment to account for loss to follow-up and fetal loss. The study will have good power to detect an 8.5% effect size, and excellent power to detect an effect size of 10% or greater.

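### As written, the parasite-density test appears to include all women, most with an implied density of zero, so it does not separate density from the incidence of placental malaria

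*Protocol*

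**What the plan says.** Under Specific Aims, aim 1 of the protocol has two safety measures: (a) the incidence of placental malaria and (b) "placental malaria parasite density". Definition of Main Endpoints makes both primary, and classes a woman with a negative placental smear as not infected.

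Under Data Analysis the general rule is: "Intent-to-treat analysis of treatment effects will be used as the primary analysis strategy for all endpoints". The density paragraph then says that placental malaria "defined as a continuous variable of parasite density will be compared between the two treatment arms", using a two-sample t-test and a Wilcoxon rank-sum test. It names no subset of women. By contrast, the paragraph on maternal anemia and maternal malaria does restrict its analysis set, to women free of the condition at baseline.

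Under Statistical Power Calculations, on incidence: "The assumed placebo arm rate of 20-30% is supported by studies reviewed above". Power for density is based on "total enrolled n=1500, with a 10% sample size adjustment to account for loss to follow-up and fetal loss", with a mean of 9000 and an SD of 5000 parasites/µL.

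**The concern.** Nothing in the density paragraph limits the comparison to infected women, and both the intent-to-treat rule and the sample size point to everyone. If smear-negative women enter with density zero, 70-80% of the values are tied at zero. A rank test on such data is driven by the share of zeros, which the incidence chi-square already tests. A t-test on such data compares incidence multiplied by mean density among the infected.

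Two things are at stake. If iron changed only incidence, aim 1(a) and aim 1(b) would usually both be significant, and one effect could be reported as two safety signals. If iron changed only density, the Wilcoxon test would mostly miss it.

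**Working it through.** **Inputs from the protocol.** 1500 × 0.90 = 1350 women, so 675 per arm (1:1 allocation is assumed; the ratio is not stated). Two-sided alpha is 0.05. Placebo incidence p is 20-30%. Density has mean m = 9000 and SD s = 5000. Zero for smear-negative women is an implication, not a written rule.

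**Step 1: the protocol's own power row.** SE = 5000 × √(2/675) = 272. A 10% change is 900, and 900/272 = 3.31, so power = Φ(3.31 − 1.96) = 91%. In the same way a 5% change gives 38% and an 8.5% change gives 80%. These match the table, but only if all 675 women per arm have densities with mean 9000 and SD 5000.

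**Step 2: do those inputs fit all women?** If a share 1 − p is zero and the overall mean is 9000, the overall SD is at least 9000 × √((1 − p)/p). That is 18,000 at p = 20% and 13,748 at p = 30%. An SD of 5000 is therefore possible only among infected women, while the sample size counts all women. The power row mixes two populations, so it does not settle which one the test uses.

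**Step 3: the t-test on all women.** Mean = pm and variance = p(m² + s²) − (pm)².
- *Density alone changes.* Take p = 25% in both arms and density 20% higher (10,800, SD 6000). The means are 2250 and 2700, and the variances 21.44 and 30.87 million. SE = √(52.31 million/675) = 278, z = 450/278 = 1.62, and power is about 37%.
- *Incidence alone changes.* Take 20% versus 26% with density unchanged. The means are 1800 and 2340, and the variances 17.96 and 22.08 million. SE = 244, z = 540/244 = 2.22, and the rejection rate is about 60%.

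**Step 4: simulation of all the tests.** 675 per arm, with lognormal density (mean 9000, SD 5000) in infected women and zero otherwise. Ranges span repeated runs.

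| Incidence, placebo vs iron | Density in infected women | t-test, all | Wilcoxon, all | Incidence chi-square | Log-density t-test, infected |
|---|---|---|---|---|---|
| equal | equal | about 5% | about 5% | about 5% | about 5% |
| 20% vs 26% | equal | 59-61% | 73-75% | 74-76% | 4-5% |
| 20% vs 30% | equal | 94-95% | 98-99% | 99% | 4-5% |
| 25% vs 25% | +20% | 37-38% | 8-10% | about 5% | 89-90% |
| 25% vs 25% | +50% | 94% | 18-22% | about 5% | about 100% |
| 20% vs 30% | 9000 vs 6000 | 4-5% | 88-89% | 99% | not needed |

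In the last row mean burden is equal (0.20 × 9000 = 0.30 × 6000 = 1800), so the t-test correctly sees no difference.

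**Step 5: sensitivity to shape.** A gamma density with the same mean and SD gives the same pattern. With a more skewed lognormal (SD twice the mean, an assumption) and 20-30% infected, a 50% rise in density is detected by the t-test in 36-54% of trials and by the Wilcoxon in 8-11%. At an incidence ratio of 0.65 with equal density, the Wilcoxon still tracks the chi-square (94-99% for both).

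**Step 6: size of the smear-positive group.** 1350 × 0.20 = 270 and 1350 × 0.30 = 405 women in total, if both arms are near the placebo rate.

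**The case against.** The strongest reply is that the all-women, zeros-included population is inferred. The density paragraph names no population, no rule scores a negative smear as zero, and the 9000/5000 inputs fit infected women. This stands, and it is why the finding is worded as what the text apparently does. It does not remove the problem. If infected women were meant, the analysis paragraph leaves that out and the power sample size is wrong.

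A reader might infer that both tests merely re-test incidence. That holds for the Wilcoxon only. The t-test validly measures mean burden. With incidence of 20-30%, it responds about equally to a 35% fall in incidence (84-97%) and a 35% fall in density (90-99%), and it detects a 50% rise in density in 94% of trials at 25% infected.

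A reader might also infer an inflated type I error from the 59-75% rejection with identical density in infected women. That is not so. Mean burden truly differs there, and both tests hold about 5% when nothing differs. The protocol nowhere states a null hypothesis about infected women only.

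Last, a reader might want density judged only in smear-positive women. That conditions on an event after randomization. For illustration, suppose iron leaves the 20% already infected unchanged and adds 6% new infections at half the density. The expected geometric mean ratio is 0.5^(6/26) = 0.85, and the smear-positive test declares a change in about 69% of trials although no woman's density fell. With the added infections at 0.7 times the density, it does so in about 26%. This objection stands and shapes the remedy.

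The lack of a rule on whether the t-test or the Wilcoxon decides is a separate matter that an analysis plan could settle. It is not relied on here.

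**Conclusion.** The concern holds in this limited form. On the plain reading of the protocol, the Wilcoxon comparison of density is close to a second incidence test: 75% against 76% rejection at 20% versus 26% infected with identical density. It has little power for density itself, about 10% at +20% and 18% at +50% with 25% infected. The t-test answers a legitimate question about mean burden, but it cannot say whether incidence or density moved. Neither result can therefore be read as a safety finding on density distinct from incidence.

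This rests on zeros for smear-negative women, 1:1 allocation, the protocol's 20-30% infection rate, and 9000/5000 as the density distribution among the infected. The Wilcoxon pattern does not depend on the distribution chosen. The t-test figures do.

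The density power row also needs revision on either reading. Under the 9000/5000 inputs, the stated 91% for a 10% change becomes about 12-16% with all women and 32-44% with infected women only.

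**What to change.** 1. State the population for the density endpoint and how a negative smear is scored.
2. Keep the all-women intent-to-treat comparison as the randomized analysis. Label it *placental parasite burden (zeros included)*, and state that it is not evidence independent of incidence.
3. Add a pre-specified two-part analysis that reports incidence in all women alongside the geometric mean ratio of density, with 95% CI, in smear-positive women.
4. State that the smear-positive part is supportive, is read jointly with incidence, and is not the sole basis for concluding that iron changes density.
5. Recompute the density power row for the population chosen.

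The cost is wording and one further regression on data already collected. The drawback is that the smear-positive part uses only about 270-405 women and can be biased if iron changes who becomes infected, so that caveat must accompany the result.

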Standard of Care: All pregnant women will receive standard prenatal care at all times. Malaria prophylaxis is provided as a dose of sulphadoxine pyremethamine at 20 weeks of gestation and one at 30 weeks of gestation. All study patients with symptomatic malaria will be managed according to the standard national policy for the treatment of malaria. Uncomplicated malaria in will be managed with oral quinine. At randomization and delivery, we will assess Hb levels. If the patient's Hb level falls below the 8.5g/dL cutoff for severe anemia, she will be treated as per standard of care in Tanzania. We will investigate the primary cause of the severe anemia and treat appropriately. For instance, if sf<12mcg/L, we will treat with iron supplementation as per standard of care. Appropriate treatment for any condition (e.g., severe malaria, pre-eclampsia) will be provided. Daily folate (400 mcg) supplementation is established as standard prenatal care practice in many developing countries including Tanzania, based on their demonstrated benefit in prevention of birth defects, particularly neural tube defects [153], and will be provided. All women who are identified to be HIV-infected during the recruitment process will be referred to an HIV/AIDS Care and Treatment clinic and provided with care and treatment, including antiretroviral therapy as needed and in accordance with national and WHO guidelines. HIV/AIDS care and treatment services are provided as part of the Harvard School of Public Health PEPFAR program that is being implemented in Dar es Salaam in collaboration with Muhimbili University and the City of Dar es Salaam Regional office of Health. In light of our recently published findings of protective effects of these multivitamins on pregnancy outcomes among HIVuninfected women, we will seek to provide such supplements to study participants after consultation with officials at the Ministry of Health.

Pharmacy Procedures and Regimen Disposal: The MAL1 study regimen will be prepared and distributed to clinic sites each week, based upon upcoming Weekly Appointment Lists. Each

Tuesday, the clinic staff will submit a Weekly Appointment List for the following week. The data unit staff will be responsible for creating and submitting Weekly Appointment Lists. The clinic research supervisor will weekly appointment lists before sent to Central Pharmacy.

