Laboratory Investigations: A peripheral venous blood sample of 10 ml will be taken from all women at screening, 20 weeks, 30 weeks, delivery, and 6 weeks post-partum. At screening, blood will be tested for a complete blood count and serum ferritin. Following randomization, the following additional assessments will be performed: ABO blood typing as part of standard prenatal care, a sickling test, a blood smear for malaria parasitemia, and c-reactive protein. Malaria parasitemia during pregnancy will be further assessed before ingestion of SP intermittent preventive therapy at 20 and 30 weeks of gestation. At delivery, the following laboratory assessments will be performed in mothers: serum ferritin, c-reactive protein, a complete blood count, and malaria parasitemia. A cord blood specimen and a placental blood specimen from drained retroplacental blood will also be collected at delivery. At the 6 week post-partum visit, malaria parsitemia will be assessed in mothers and a 1 ml specimen will be drawn from the infants through venipuncture for a peripheral blood smear for malaria and a complete blood count. If venipuncture is unsuccessful, however, the heel stick method will be used as an alternative.

Peripheral thick blood smears will be stained with Giemsa and then examined for parasites. Parasite species and density will be recorded. The presence or absence of asexual forms of parasites will be recorded, and the density of such stages will be recorded. Slides will be examined without knowledge of clinical malaria status. In addition, qualitative and quantitative PCR for malaria will be performed at delivery for mothers and at 6 weeks post partum for infants.

After delivery, the placenta will be brought to the laboratory in a sealed plastic bucket containing 500 ml normal saline. A 1 cm3 biopsy will be taken from the maternal side of the placenta

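### The Hemoglobin analysis paragraph counts on a 30-week haemoglobin that the care and laboratory sections do not schedule, so the Hb <8.5 g/dL treatment rule may have no planned check before delivery

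*Protocol*

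**What the plan says.** The Hemoglobin paragraph under Data Analysis gives three time points: "This parameter will be assessed three times (at baseline, 30 weeks of pregnancy and at delivery". The primary comparison uses two of them: "In the primary analyses we will compare the mean change between baseline and delivery".

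Standard of Care names two: "At randomization and delivery, we will assess Hb levels". It then requires treatment if Hb falls below 8.5 g/dL, after the cause has been looked for: "For instance, if sf<12mcg/L, we will treat with iron supplementation as per standard of care". Item (2) of Human Subjects repeats the rule.

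Laboratory Investigations states that Hb is obtained from the complete blood count. For mothers it places that count at entry ("At screening, blood will be tested for a complete blood count and serum ferritin") and at the end ("At delivery, the following laboratory assessments will be performed in mothers: serum ferritin, c-reactive protein, a complete blood count, and malaria parasitemia"). Blood is drawn in between ("A peripheral venous blood sample of 10 ml will be taken from all women at screening, 20 weeks, 30 weeks, delivery"), but the only test named for the mid-pregnancy samples is the malaria smear: "Malaria parasitemia during pregnancy will be further assessed before ingestion of SP intermittent preventive therapy at 20 and 30 weeks of gestation".

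In the schedule table, the Maternal Hemogram row is marked at enrolment/randomisation and at delivery only.

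**The concern.** A site works from the care and laboratory sections and the schedule table. Staff who follow those will not run a blood count at 30 weeks, although the analysis section treats one as part of the plan.

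The larger issue is the treatment rule. The trial withholds iron from half its participants, and women with Hb between 8.5 and 11.0 g/dL may enrol. The rule for Hb below 8.5 g/dL protects a woman whose Hb drops during follow-up, but it can act only on a measured value. Clinical Parameters lists no Hb among the monthly assessments. With Hb scheduled only at entry and delivery, the first planned opportunity to trigger the rule comes when the study tablets stop. Before that, detection in either arm depends on symptoms or examination.

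The protocol also does not say at which visits the secondary endpoint of maternal anaemia is ascertained, so its capture may depend on the same question.

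**Working it through.** **Step 1. The sections side by side**

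| Section of the protocol | Maternal Hb or blood count | Anything else at 20 and 30 weeks |
|---|---|---|
| Data Analysis, Hemoglobin | baseline, 30 weeks, delivery | – |
| Standard of Care | randomisation, delivery | – |
| Laboratory Investigations | screening, delivery | 10 ml sample; malaria parasitaemia named |
| Schedule table | enrolment/randomisation, delivery | malaria smear marked |
| Clinical Parameters (monthly visits) | none listed | – |
| Human Subjects (2) | treatment rule, no Hb test named | blood sample drawn |

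The first row gives three measurements; the next three rows give two. The smear row of the schedule table is marked at 20 and 30 weeks while the hemogram row is not, so the blank is unlikely to be a lost column. The table is supporting evidence only: its Screening column is empty for every laboratory test, although Laboratory Investigations requires some then. The contradiction stands without it.

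**Step 2. Is the primary Hb analysis touched?**

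The power table assumes mean 11.4 g/dL, SD 3.8, two-sided alpha 0.05 and 1,500 women with 10% loss, so n = 1,500 × 0.9 / 2 = 675 per arm. A 5% change is 0.05 × 11.4 = 0.57 g/dL. The two-sample normal approximation gives 78.7%, against 79% stated. The smallest difference detectable with 80% power is 0.579 g/dL, or 5.08%, against 5.0% stated. Both reproduce. Neither uses the 30-week value, so the conflict leaves them unchanged.

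**Step 3. Longest interval without a scheduled Hb**

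Assumption: delivery at week D = 40, range 37 to 41. With entry at week E:

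- two measurements: gap = D − E
- with a 30-week count: longest gap = max(30 − E, D − 30)

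| Entry week E (source) | Two measurements | With a 30-week count |
|---|---|---|
| 12 (lower end of the 12 to 19 week band in Study Population Characteristics) | 40 − 12 = 28 (25 to 29) | max(18, 10) = 18 (18 to 18) |
| 20 (latest randomisation in Eligibility criteria; approximate average in Dietary Assessment) | 40 − 20 = 20 (17 to 21) | max(10, 10) = 10 (10 to 11) |
| 21.4 (median in earlier trials, Study Population Characteristics) | 40 − 21.4 = 18.6 (15.6 to 19.6) | max(8.6, 10) = 10 (8.6 to 11) |
| 27 (upper limit in Eligibility criteria) | 40 − 27 = 13 (10 to 14) | max(3, 10) = 10 (7 to 11) |

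Eligibility criteria gives both 20 and 27 weeks as limits, so the entry distribution is uncertain. In the earlier trials close to half the women entered at 12 to 19 weeks; the earliest of them would keep a long gap even with the added count.

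**The case against.** The strongest reply is that the sections can be reconciled. Standard of Care does not say that Hb is measured only at randomisation and delivery, and Laboratory Investigations does not call its list exhaustive. Human Subjects (2) states the treatment rule directly after scheduling blood at 20 and 30 weeks, and ends by saying the laboratory data will also guide clinical care. On that reading the analysis paragraph simply adds a time point. This is possible, but no operational section names an Hb or blood count on those samples, and the 30-week sample has another stated use. A site cannot be expected to infer a test that is not listed.

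A second reply is that nothing analytic depends on the 30-week value and that the safety gap is unquantified. Both are true. The primary analysis and its power stand, no analysis explicitly uses the 30-week Hb, and the protocol gives no rate of Hb below 8.5 g/dL. Monthly examinations, standard prenatal care and open access to the clinic also allow prompted tests. These limit the consequence, but they are not a scheduled check.

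A third reply is that finding more cases means more open-label iron in the placebo arm and a smaller contrast. As a crude worst case, suppose 10% of placebo women were treated and all gained the full effect. The difference would fall to 0.57 × 0.9 = 0.513 g/dL, and power from about 79% to about 70%. That requires every such woman to have ferritin below 12 µg/L and to gain the whole effect in what remains of pregnancy after 30 weeks. The Introduction describes anaemia in this population as multifactorial, so the real loss should be smaller. The protocol's own rule already accepts that these women are treated.

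**Conclusion.** The concern holds. The current text gives two incompatible schedules for a primary endpoint variable and does not say which governs. If the analysis paragraph governs, there is one scheduled Hb in pregnancy after entry. If the care and laboratory sections govern, there is none, and the Hb <8.5 g/dL rule has no planned measurement for roughly 13 to 28 weeks, for entry at 27 down to 12 weeks and delivery at an assumed 40 weeks.

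These are intervals, not harm: the number of women who would cross 8.5 g/dL cannot be derived from the protocol. The point should be fixed because it bears on a safety rule in a placebo-controlled iron trial and the remedy is cheap. It does not threaten the primary Hb result.

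**What to change.** Add a complete blood count at 30 weeks, on the 10 ml sample already drawn, to Standard of Care, Laboratory Investigations and the Maternal Hemogram row of the schedule table, so that they match the Hemoglobin analysis paragraph. State that ferritin is run on the same sample when Hb is below 8.5 g/dL. Standard of Care already makes iron depend on ferritin, so this spells out what the rule needs.

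Cost:

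- **Blood counts:** one per woman still followed at 30 weeks, from 1,500 × 0.85 = 1,275 (lower retention figure under Limitations, with all loss before 30 weeks) to 1,500 (no loss before then). No extra visit or needle.
- **Reflex ferritin:** assuming 1% to 10% of women are below 8.5 g/dL at 30 weeks, 1,275 × 0.01 ≈ 13 to 1,500 × 0.10 = 150 tests.
- **Treatment contrast:** under the same assumption, at most 637.5 × 0.01 ≈ 6 to 750 × 0.10 = 75 placebo women could start open-label iron before delivery, and fewer once the ferritin condition is applied.
- **Design:** no change to the planned primary Hb comparison or the sample size.

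Deleting the 30-week time point from the analysis paragraph would also remove the contradiction, at no cost, but would leave the treatment rule without a scheduled check during pregnancy. Adding the count is the better choice.
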